## 2.5 Study Rationale

AUR101 is a potent and selective inhibitor of ROR $\gamma$  with good cellular activity in Th17 differentiation assays. The compound has also demonstrated good efficacy in relevant animal models. Toxicology studies with the compound have also demonstrated a favorable safety profile at the exposures showing efficacy in animal models. A completed FIH study has determined a desirable safety, PK and optimal IL-17 inhibition, when AUR101 is administered at 600 mg BID.

In view of favorable preclinical safety, preclinical efficacy, and PK, PD and safety data derived from FIH study, the current Phase II Proof of Concept (POC) study has been planned in moderate-to-severe psoriasis.

## 3.0 STUDY OBJECTIVES AND ENDPOINTS

### 3.1.1 Primary Objectives

The primary objective of the study is to assess efficacy of AUR101 in patients with moderate-to-severe psoriasis.

### 3.1.2 Secondary Objectives

The secondary objectives of the study are as follows,

**Title: Statistical Analysis Plan-Module I**

 SOP Number:  
 JSS-DM-BIS-01

Current Version Number: 1.0

Previous Version Number: Nil

 Document Date:  
 25MAR2021

1. To evaluate the safety and tolerability of two oral doses of AUR101 in patients with moderate-to-severe psoriasis.
2. To evaluate the plasma pharmacokinetics of AUR101 in patients with moderate-to-severe psoriasis
3. To evaluate effect of AUR101 on quality of life in patients with moderate-to-severe psoriasis.

### 3.2.0 End Points

#### 3.2.1 Primary Endpoint(s)

Proportion of patients achieving PASI 75 (i.e. 75% reduction from baseline PASI score) at the end of week 12.

#### 3.2.2 Secondary Endpoint(s)

1. Proportion of patients achieving PASI 75 (i.e. 75% reduction from baseline PASI score) at the end of week 4 and 8.
2. Proportion of patients achieving PASI 50 (i.e. 50% reduction from baseline PASI score) at week 4, 8 and 12.
3. Proportion of patients achieving IGA 0 or 1 at week 4, 8 and 12.
4. Percent change from baseline in PASI score at week 4, 8 and 12
5. Change from baseline in IGA scale at week 4, 8 and 12
6. Change from baseline to week 4, 8 and 12 in percent Body Surface Area (BSA) involved
7. Change from baseline to week 4, 8 and 12 in Dermatology Life Quality Index (DLQI)

#### 3.2.3 Secondary Safety Endpoint

Safety will be evaluated based on the nature and incidence of treatment emergent adverse events (AEs), vital signs, electrocardiograms (ECGs), laboratory assessments and physical examinations in patients treated with AUR101 or placebo.

#### 3.2.4 Pharmacokinetic Endpoints

**Title: Statistical Analysis Plan-Module I**

SOP Number:  
JSS-DM-BIS-01

Current Version Number: 1.0

Previous Version Number: Nil

Document Date:  
25MAR2021

Individual plasma PK parameters, including but not limited to  $t_{1/2}$ ,  $AUC_{0-12}$ ,  $K_{el}$ , and  $CL/F$ .  $C_{max}$ , and  $T_{max}$  will be estimated using appropriate compartmental or noncompartmental models. Summaries of PK parameters will be presented by dose group.

### 3.2.5 Exploratory Endpoints

While not stated in the study protocol, the sponsor will also explore the effects of AUR101 on PASI-90 as well as PASI-100 in the study.

### 3.2.6 Efficacy & Safety Evaluation score description

#### 3.2.6.1 PASI (Psoriasis Area and Severity Index)

PASI is widely used tool to measure the severity of psoriasis. It combines area of the lesions with severity of individual lesions by grading erythema, induration/thickness and scaling. It can be 0 (minimum) to 72 (maximum). A PASI score will be derived as indicated in Table 1.

The following definitions are used in this study according to Committee for medicinal products for human use (CHMP) guidelines:

- ☐ PASI 75 response: patients achieving  $\geq 75\%$  improvement (reduction) in PASI score compared to baseline are defined as PASI 75 responders
- ☐ PASI 50 response (partial response): patients achieving  $\geq 50\%$  improvement (reduction) in PASI score compared to baseline are defined as PASI 50 responders.
- PASI 90 response: patients achieving  $\geq 90\%$  improvement (reduction) in PASI score compared to baseline are defined as PASI 90 responders
- PASI 100 response: patients achieving 100% improvement (reduction) in PASI score (i.e. achieving PASI score of 0) compared to baseline are defined as PASI 100 responders.

**Table 1. Psoriasis Area and Severity Index**

Body part	Erythema (E)	Thickening (plaque elevation, induration, I)	Scaling (desquamation, D)	Area score (based on true area %)#
Head (H) including neck	0=none 1=slight	0=none 1=slight	0=none 1=slight	0 = 0% 1 = 1% - 9%

**Title: Statistical Analysis Plan-Module I**

 SOP Number:  
 JSS-DM-BIS-01

Current Version Number: 1.0

Previous Version Number: Nil

 Document Date:  
 25MAR2021

	2=moderate 3=severe 4=very severe	2=moderate 3=severe 4=very severe	2=moderate 3=severe 4=very severe	2 = 10% - 29% 3 = 30% - 49% 4 = 50% - 69% 5 = 70% - 89% 6 = 90% - 100%
Trunk (T) Including axilla and groin area	0=none 1=slight 2=moderate 3=severe 4=very severe	0=none 1=slight 2=moderate 3=severe 4=very severe	0=none 1=slight 2=moderate 3=severe 4=very severe	0 = 0% 1 = 1% - 9% 2 = 10% - 29% 3 = 30% - 49% 4 = 50% - 69% 5 = 70% - 89% 6 = 90% - 100%
Upper Limbs (U)	0=none 1=slight 2=moderate 3=severe 4=very severe	0=none 1=slight 2=moderate 3=severe 4=very severe	0=none 1=slight 2=moderate 3=severe 4=very severe	0 = 0% 1 = 1% - 9% 2 = 10% - 29% 3 = 30% - 49% 4 = 50% - 69% 5 = 70% - 89% 6 = 90% - 100%
Lower Limbs (L) Including buttocks area	0=none 1=slight 2=moderate 3=severe 4=very severe	0=none 1=slight 2=moderate 3=severe 4=very severe	0=none 1=slight 2=moderate 3=severe 4=very severe	0 = 0% 1 = 1% - 9% 2 = 10% - 29% 3 = 30% - 49% 4 = 50% - 69% 5 = 70% - 89% 6 = 90% - 100%

**#Percentage (not score) of body region (not whole body) affected will be recorded.**

	JSS Medical Research India Private Limited Data Management		
Title: Statistical Analysis Plan-Module I			
SOP Number: JSS-DM-BIS-01	Current Version Number: 1.0	Previous Version Number: Nil	Document Date: 25MAR2021

### 3.2.6.2 Investigator Global Assessment (IGA)

The 5-point IGA mod 2011 rating scale is provided in Table 2. Based on this scale, a patient will be considered as IGA responder if the patient achieves a score of 0 or 1 and improves by at least 2 points on the IGA scale compared to baseline.

**Table 2. Investigator Global Assessment**

Score	Short Descriptor	Detailed Description
0	Clear	No signs of psoriasis; post-inflammatory hyperpigmentation may be present
1	Almost Clear	No thickening; normal to pink coloration; no to minimal focal scaling
2	Mild	Just detectable to mild thickening; pink to light red coloration; predominantly fine scaling
3	Moderate	Clearly distinguishable to moderate thickening; dull to bright red, clearly distinguishable to moderate thickening; moderate scaling
4	Severe	Severe thickening with hard edges; bright to deep dark red coloration; severe/coarse scaling covering almost all or all lesions

### 3.2.6.3 Dermatology Life Quality Index (DLQI)

The Dermatology Life Quality Index (DLQI) is a 10-item general dermatology disability index designed to assess health-related quality of life in adult patients with skin diseases such as eczema, psoriasis, acne, and viral warts. Scores range from 0 to 30, and higher scores indicate greater health-related quality-of life impairment. Additionally, each subscale of the DLQI may be analyzed separately. In DLQI score, Minimal Clinically Important Difference (MCID) is considered as 5-points reduction from baseline. [7-8]

## 4.0 STUDY METHODS

### 4.1 Study Design and Plan

This is a multicenter, double-blind, double-dummy, placebo controlled, randomized study to evaluate efficacy and safety of two doses of AUR101 in patients with moderate-to-severe psoriasis. There are three arms – two arms of AUR101 (400 and 600 mg BID) and one arm of placebo.

	JSS Medical Research India Private Limited Data Management		
Title: Statistical Analysis Plan-Module I			
SOP Number: JSS-DM-BIS-01	Current Version Number: 1.0	Previous Version Number: Nil	Document Date: 25MAR2021

All the patients are followed up for  $14 \pm 2$  days of their last dose for safety assessment.

A subset up to 25 consenting patients will participate in the pharmacokinetic part in addition to main study. Separate consent will be taken. If patient consents for PK, samples will be collected at week 4 ( $\pm 2$  days) visit of dosing.

#### 4.1.1 Number of Patients and Duration of Treatment

Approximately 90 patients with chronic moderate-to-severe chronic plaque psoriasis are randomized to each of the three arms (1:1:1) by IWRS as mentioned below:

- AUR101 400 mg BID
- AUR101 600 mg BID
- Placebo BID

All the patients will receive study drugs for 12 weeks in a double blind, double dummy fashion.

#### 4.1.2 Formulation and Mode of Administration

AUR101 is formulated as 100 and 300 mg film coated tablets. Patients will take study drugs orally with water, twice daily after meals (breakfast and dinner), preferably same time each day.

#### 4.2 Study Initiation and Completion

This study is of approximately of 14 weeks from the screening through end of study. There will be seven scheduled visits and one follow up visit in the study. Follow-up visit will be  $14 \pm 2$  days after last dose tablet taken by the patients.

#### 4.3 Selection of Study Population

Adult males or females of age group between (18-65) years and confirmed diagnosis of chronic plaque-type psoriasis at least moderate severity, defined as (Psoriasis Area and Severity Index)  $PASI \geq 12$  and involved Body Surface Area (BSA)  $\geq 10$  % at screening, diagnosed at least 6 months before screening and have willingness to give written informed consent and ability to adhere to the study restrictions and assessments schedule.

	JSS Medical Research India Private Limited Data Management		
Title: Statistical Analysis Plan-Module I			
SOP Number: JSS-DM-BIS-01	Current Version Number: 1.0	Previous Version Number: Nil	Document Date: 25MAR2021

#### 4.3.1 Screened Population

The population will include all patients in the study who have signed Inform Consent Form.

#### 4.3.2 Randomized Population

The Population will include all patients in the study who have signed Inform Consent Form and satisfied all inclusion and exclusion criteria.

#### 4.3.3 Safety Population

The Safety Population will include all patients in the study who receive at least one dose of study treatment.

#### 4.3.4 Efficacy population

Efficacy population will include patients who

- have a valid baseline and at least one post-baseline (follow up) assessment for
- PASI score by the independent dermatologist or withdrawal is associated with lack of effect by the patient before post-baseline assessment.
- do not have any major protocol or inclusion/exclusion violations,

Efficacy population will provide sample for analysis of primary, secondary and exploratory endpoints. For patients who dropped out during study treatment period due to any reason, data from the last efficacy assessment will be considered for the primary endpoint and other secondary efficacy endpoints relevant at other future time-points as per Last Observation Carried Forward (LOCF) approach.

Efficacy data collected solely based on the photographs without on-site examination by the investigator/independent dermatologist will not be considered for the analysis and this data will also be imputed with LOCF approach.

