11.3.2 Efficacy Population

Efficacy population will include patients who do not have any major protocol or inclusion/exclusion violations, have a valid baseline and at least one post-baseline (follow up) assessment for PASI score by the independent dermatologist.

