#### 4.3.5 Major Protocol Deviations

The protocol deviations in the study will be evaluated on a case-to-case basis and will be categorized as major or minor. A major protocol deviation is defined as any deviation that may affect the efficacy outcome or patient's safety. Subjects having major protocol deviation will be finalized prior to the soft lock.

Following are some protocol deviations.

1. Violation of major inclusion/ exclusion criteria assessment

**JSS Medical Research India Private Limited  
Data Management**

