**Title: Statistical Analysis Plan-Module I**

SOP Number:  
JSS-DM-BIS-01

Current Version Number: 1.0

Previous Version Number: Nil

Document Date:  
25MAR2021

2. Use of prohibited concomitant medication
3. Treatment non-compliance
4. Non-compliance/non-assessment of study procedure
5. Visit out of the window period

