#### 5.4 Methods for Withdrawals, Missing Data, and Outliers

In case of a patient's withdrawal from the study without any major protocol deviation, its values on subsequent visits will be considered missing.

The last observation carried forward (LOCF) method will be applied to all efficacy measurements (PASI score, IGA mod 2011 score, DLQI score etc.) when at least one post-baseline assessment is available. If all post baseline efficacy values are missing for one efficacy parameter then these missing values will not be imputed and this patient will be removed from the analysis of the corresponding variable, i.e. it might be that the number of patients providing data for one variable is smaller than efficacy population. If withdrawal prior to first post-baseline assessment is considered due to lack of effect of the study drug by the investigator, then the respective patient will be considered as non-responder in PASI and IGA responder analysis, and no change (i.e. post-baseline difference of 0) will be considered for percent or absolute change in PASI, IGA or DLQI parameters.

For missing safety variables, when repeat assessment data is available for the respective visit, then these repeat assessment data will be imputed. E.g. The hematology parameters are not available for Visit 4 for any patient and repeat hematology assessment is done prior to next scheduled visit, then hematology parameters during Visit 4 will be replaced with repeat assessment parameters. However, no values will be replaced if the parameter value is available. For example, if only ALT and AST are not available for a specific visit in biochemistry panel and repeat assessment prior to next visit is done with all liver function tests (ALT, AST, ALP, bilirubin, etc.), then only ALT and AST values will be replaced and other liver function values will not be replaced.

For the efficacy variables (PASI score, IGA mod 2011 score, DLQI score), no observed values will be considered as outliers. For safety parameters like vital signs, lab parameters etc., any value which is out of range will be summarized as observed. However, it will be checked whether it is a normal or abnormal finding and will be

	JSS Medical Research India Private Limited Data Management		
Title: Statistical Analysis Plan-Module I			
SOP Number: JSS-DM-BIS-01	Current Version Number: 1.0	Previous Version Number: Nil	Document Date: 25MAR2021

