## 7.0 EFFICACY ANALYSES

### 7.1 Primary Efficacy Analysis

Summary statistics with 95% confidence interval will be presented for PASI. Comparison of percentage of patients achieving at least 75% reduction from Baseline

	JSS Medical Research India Private Limited Data Management		
Title: Statistical Analysis Plan-Module I			
SOP Number: JSS-DM-BIS-01	Current Version Number: 1.0	Previous Version Number: Nil	Document Date: 25MAR2021

PASI score (PASI-75) to Week 12 between treatment arm and placebo will be evaluated using Chi-square/Fisher's exact test with responder and non-responder psoriasis type. Also, 95% CI for the responders within treatment will be evaluated by using Clopper-Pearson method and 95% CI for treatment difference will be evaluated by using Miettinen-Nurminen method.

Additional sensitivity analysis will be tested by using Cochran-Mantel-Haenszel (CMH) test after adjusting the sites and baseline PASI score. The analysis will be performed on efficacy population. No multiplicity adjustments will be done for the primary analysis.

Two sets hypotheses will be tested,

1.  $H_0: P_1=P_0$  vs  $H_1: P_1 \neq P_0$
2.  $H_0: P_2=P_0$  vs  $H_1: P_2 \neq P_0$

Where,  $P_0$ ,  $P_1$  and  $P_2$  are the proportion of responders in placebo, 400 mg and 600 mg arms, respectively. Since, both hypotheses will be tested separately, no multiplicity adjustment will be done.

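### The only efficacy set drops patients for major deviations that can arise after randomisation, and no efficacy analysis of all randomised or all treated patients is planned

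*SAP*

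**What the plan says.** SAP 4.3.4 defines one efficacy population and assigns it the primary, secondary and exploratory endpoints. Its members must "do not have any major protocol or inclusion/exclusion violations". They also need a valid baseline and at least one later PASI by the independent dermatologist, or a withdrawal for lack of effect before that assessment. SAP 7.1, which contains both the primary test and the CMH sensitivity test, states: "The analysis will be performed on efficacy population". Protocol 11.3.2 has the same exclusion: "Efficacy population will include patients who do not have any major protocol or inclusion/exclusion violations".

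SAP 4.3.5 gives the criterion: "A major protocol deviation is defined as any deviation that may affect the efficacy outcome", or patient safety. Grading as major or minor is case by case, and the list is finalised before soft lock. The listed candidates are eligibility violations, "Use of prohibited concomitant medication", non-compliance with treatment, non-compliance with or missed study procedures, and out-of-window visits.

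Two wider sets exist, but neither has an efficacy analysis:

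- **Randomized Population (SAP 4.3.2):** defined as patients who consented and "satisfied all inclusion and exclusion criteria", so by eligibility and not by randomisation.
- **Safety Population:** used for safety, compliance, medications and medical history.

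For patients with no post-baseline value of a parameter, SAP 5.4 says "this patient will be removed from the analysis of the corresponding variable". The exception is early withdrawal that the investigator attributes to lack of effect. Such a patient is a PASI and IGA non-responder, and zero change "will be considered for percent or absolute change in PASI, IGA or DLQI parameters".

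**The concern.** The set is a hybrid. It keeps dropouts through LOCF, and Protocol 11.4.1.3 invokes the intent-to-treat principle to link follow-up data to missed visits. Yet it removes patients for conduct after randomisation. A patient who is not improving may take a prohibited psoriasis treatment or stop taking tablets. Protocol 8.11 discontinues patients for prohibited medication, and SAP 4.3.4 could then delete them from the analysis, although they are plausibly non-responders.

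The rate of such events can differ by arm. Losing non-responders from an active arm raises the estimated effect, and losing them from placebo lowers it. The CMH analysis changes the method but not the patients, so it would show neither.

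The requirement for a post-baseline PASI matters less. Withdrawn patients are asked back for a follow-up visit that includes a PASI (Protocol 6.4.4, 7.4), so few should be lost this way.

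Two rescue points touch the same set:

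- **Membership.** Protocol 8.13 and SAP 4.6 call rescued patients treatment failures, and Protocol 7.3 lists rescue separately from major deviation. Both imply that rescued patients stay in the set, but the SAP does not say so. Rescue can be a biologic, a class prohibited in Protocol 8.11, and prohibited medication is a listed deviation.
- **Scoring.** The synopsis scores rescue as failure with LOCF; Protocol 8.13 and SAP 4.6 say failure only. These must be reconciled.

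**Working it through.** **Inputs from the documents.** PASI 75 rates of 7% (placebo) and 35% (active), 25 per arm raised to 30 for 15-20% dropout, 80% power, one-sided 0.05 (Protocol 11.1, SAP 5.1). SAP 7.1 names chi-square/Fisher's exact with two-sided hypotheses, and SAP 9.1 uses p<0.05.

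**Assumptions.** The number excluded (k), that all those excluded are non-responders, that they come from one arm, and an alternative active rate of 25%.

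**The plan's own figure.** With n=25 and pooled rate 0.21:

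z = [√25 × 0.28 − 1.645 × √(2 × 0.21 × 0.79)] / √(0.07 × 0.93 + 0.35 × 0.65) = (1.400 − 0.948) / 0.541 = 0.84, so power is 79.9%.

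The stated 80% is reproduced. The concern does not depend on it.

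**Effect on a single result.** Uncorrected chi-square: z = (a/n₁ − b/n₀) / √[p̄(1−p̄)(1/n₁ + 1/n₀)], two-sided.

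| Active v placebo | Difference (points) | Chi-square p | Fisher p |
|---|---|---|---|
| 8/30 v 2/30 | 20.0 | 0.038 | 0.080 |
| 8/25 v 2/30 (5 dropped from active) | 25.3 | 0.015 | 0.032 |
| 8/30 v 2/25 (5 dropped from placebo) | 18.7 | 0.074 | 0.092 |
| 10/30 v 2/30 | 26.7 | 0.010 | 0.021 |
| 10/25 v 2/30 (5 dropped from active) | 33.3 | 0.003 | 0.007 |
| 10/30 v 2/25 (5 dropped from placebo) | 25.3 | 0.024 | 0.046 |

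The estimate moves in every case. The verdict changes only near the threshold.

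**How often a result is that close.** Sum over all outcomes of Bin(30, p₁) and Bin(30, 0.07), counting p<0.05 by chi-square with active better, before and after removing k non-responders from one arm. Power before removal is 79.8% at p₁=35% and 50.0% at p₁=25%.

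| Active rate | k | Verdict gained (dropped from active) | Verdict lost (dropped from placebo) |
|---|---|---|---|
| 35% | 1 | 2.7% | 0.5% |
| 35% | 3 | 6.8% | 5.8% |
| 35% | 5 | 10.5% | 10.4% |
| 25% | 3 | 8.4% | 8.8% |
| 25% | 5 | 15.5% | 11.7% |

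**Cost of keeping patients without data.** Power at 35% v 7%, two-sided 0.05 chi-square, with k per arm lacking a post-baseline PASI:

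| k per arm | Counted as non-responders (of 30) | Excluded (27 or 24 per arm) | Cost (points) |
|---|---|---|---|
| 3 | 74.9% | 77.7% | 2.8 |
| 6 (20% of 30) | 69.3% | 71.7% | 2.4 |

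**The case against.** The strongest reply concerns size.

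- **Worst case.** The illustrations put every exclusion in one arm and make every excluded patient a non-responder. If those excluded respond like those kept, there is no systematic shift.
- **False positives.** At 7% in both arms, removing 3 or 5 active non-responders moves the chance of a significant result favouring active from 2.2% only to 2.3% or 3.3%. Removing 5 from each arm leaves it at 2.2%. At an assumed 20% in both arms the inflation is larger: one-sided 0.05 error rises from 5.5% to 8.0% or 10.7%.
- **Choice of test.** By Fisher, 8/30 v 2/30 is not significant to begin with, so the placebo exclusion changes no verdict. But the active exclusion then makes it significant (0.080 to 0.032). By Fisher, even one active exclusion gains significance in 9.7% of trials at the design rates, against 2.7% by chi-square.
- **Safeguards.** The trial is double-blind, the randomisation list is held by an independent statistician (Protocol 8.4.1), and the deviation list is fixed before soft lock. SAP 4.3.5 does not say that any listed item must exclude a patient.
- **Context.** This is a proof-of-concept study, and a supportive all-treated analysis might be enough.

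These points limit the likely size and are accepted to that extent. They do not supply a missing analysis. Blinded classification, which the SAP does not state, would still not cure exclusions that depend on treatment. SAP 1.0 also foresees use of the results for a sample-size change, publication and regulatory submission, which is more than an internal signal.

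**Conclusion.** The concern holds. All efficacy results rest on one set from which patients can be removed for events after randomisation, under a criterion tied to the efficacy outcome, and no planned analysis would expose the consequence. The actual size cannot be known from the documents. Under the assumptions shown, one exclusion rarely matters by chi-square, while three to five in one arm change the verdict in about 6% to 16% of trials across the two active rates. A clear result, such as 10/30 v 2/30, keeps its verdict. This should be fixed before unblinding; it does not by itself invalidate the trial.

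**What to change.** 1. Make the primary efficacy set all randomised patients who took at least one dose, analysed as randomised. Keep the present set as a supportive per-protocol analysis, and record the change from Protocol 11.3.2.
2. For all PASI and IGA responder endpoints, count patients with rescue or prohibited psoriasis medication as non-responders from that point on. Count patients with no post-baseline assessment as non-responders at every visit, and apply this no-data rule to the DLQI responder endpoints in SAP 7.3 too.
3. For continuous endpoints, extend the SAP 5.4 no-change rule from lack-of-effect withdrawals to all patients without post-baseline data, and add BSA.
4. Keep patients with other deviations in, with their observed data and the SAP 5.4 LOCF rule. State whether the follow-up linkage in Protocol 11.4.1.3 still applies.
5. Define the Randomized Population as all patients randomised. Patients later replaced under Protocol 7.5 remain in it, so an arm may exceed 30.
6. State that deviations are classified blind to treatment.
7. State that rescue is not an excluding deviation, and reconcile failure with LOCF across the synopsis, Protocol 8.13 and SAP 4.6.

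The cost is SAP wording and one extra set of efficacy tables, with no new data. The observed active response rate may be lower. Against excluding the same patients, the power loss is under 3 points in the cases computed.

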8.11 Prohibited Concomitant Medications

Use of any treatments that could confound the efficacy are not allowed during the study for any indication. Following drugs are not allowed during the study period:

- Treatment with topical corticosteroid, topical vitamin D analogues, pimecrolimus, tacrolimus, retinoids, salicylic acid, lactic acid, tar, urea, α -hydroxy or fruit acids
- Treatment with systemic corticosteroids or non-steroidal systemic immunosuppressive or immunomodulator drugs (e.g., cyclosporine, methotrexate, mycophenolate-mofetil, azathioprine, etc.) or phototherapy
- Treatment with any drug, including any biological immunomodulating agents like adalimumab, etanercept, secukinumab, ustekinumab etc. which can affect psoriasis

If the investigator use of any of above treatments is required, then the patient should not be randomized into the study. Additionally, any live virus vaccination during the study is not permitted.

If a patient receives any prohibited medication or live virus vaccination during the study period, he/she should be discontinued from the study by the investigator after consultation with sponsor medical monitor. Withdrawal procedures as mentioned in section 7.4 should be performed.

Patients are also advised to avoid extreme long exposures to sunlight like sun-bathing

during the study period.

If patient has received any of the above-mentioned therapy before randomization, adequate gap between initiation of study treatment and last dose of prohibited medication should be ensured as mentioned in exclusion criteria no. 5 to 8.

Whenever in doubt about confounding, investigators are recommended to discuss with sponsor medical monitor before starting any new drug during the study period.

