9.5 Sequence of Assessments

During treatment visits (Visit 2 to 7), following sequence of assessments should be followed at the site:

- Patient related questionnaire DLQI filling
- PASI, involved BSA and IGA assessment by Independent dermatologist
- PASI, involved BSA and IGA assessment by investigator
- Clinical examination, vitals, medical history, concomitant medication, AE assessment, photography and other study related procedures mentioned in Table 1
- IP compliance check (Visit 3 onwards)
- IP dispense according to IWRS
- Dosing at the site followed by PK sampling in consenting patients at week 4 (±2 days) visit.

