#### 4.6 Rescue Medication

Rescue medication can be given if patient’s PASI score is increasing by at least 50% from baseline level at or after 6 weeks of therapy. In addition to above, if a patient has intolerable symptoms from psoriasis, then any available medication, including any biologic medications, such as secukinumab or adalimumab, can be administered as rescue medications.

Patients who receive rescue treatment during the study treatment period will be considered treatment failures for the purpose of efficacy analysis. To conduct efficacy and safety assessments (e.g. disease severity scores, safety labs) immediately before administering any rescue treatment. Patients who receive “Rescue Medication” will be discontinued from the trial. All such patients should be followed up after 14 ±2 days of study drug discontinuation for safety assessment.

	JSS Medical Research India Private Limited Data Management		
Title: Statistical Analysis Plan-Module I			
SOP Number: JSS-DM-BIS-01	Current Version Number: 1.0	Previous Version Number: Nil	Document Date: 25MAR2021

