### 5.1 Sample Size Determination

AUR101 doses will be tested versus placebo with respect to the primary endpoint (PASI 75 response). A sample size of 25 in each of the three arms will provide an 80% power with a one-sided Type I error of 0.05, if the true placebo response rate is 7% and the response rate on investigational arm(s) is 35%. The sample size is increased to 30 to account for ~ 15-20% dropouts over the study period. Placebo response rates from previous studies was 4-7% in most of the studies in similar patient population. No multiplicity adjustments were considered in the sample size calculation as it is a POC study.

A subset of approximately 25 consenting patients will participate in the pharmacokinetic part in addition to main study.

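### An anti-psoriatic drug makes a patient a treatment failure only if it is given as rescue; taken otherwise, it probably leads to exclusion and can lead to a score on that drug being carried to Week 12

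*SAP*

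**What the plan says.** **Rescue.** SAP 4.6 states: "Patients who receive rescue treatment during the study treatment period will be considered treatment failures for the purpose of efficacy analysis". Protocol 8.13 says the same. Both allow any available drug as rescue and give secukinumab and adalimumab as examples.

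**Prohibited medication.** Protocol 8.11 names those same two agents among the drugs not allowed during the study. Its consequence concerns conduct only: "If a patient receives any prohibited medication or live virus vaccination during the study period, he/she should be discontinued from the study", after consultation with the medical monitor. It gives no endpoint outcome.

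**Deviations.** SAP 4.3.5 lists "Use of prohibited concomitant medication" among its examples. Each deviation is judged individually as major or minor before soft lock, and major means that it could influence the efficacy result or safety. SAP 4.3.4 and Protocol 11.3.2 remove patients with major violations from the efficacy population, on which SAP 7.1 runs the primary analysis.

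**Dropouts who stay in.** SAP 4.3.4 applies LOCF in these words: "For patients who dropped out during study treatment period due to any reason, data from the last efficacy assessment will be considered for the primary". Protocol 11.4.1.3 also lets efficacy data from follow-up fill missed visits, and Table 1 schedules PASI at follow-up.

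**Order of assessments.** In Protocol 9.5 both sets of PASI and IGA ratings come before this step: "Clinical examination, vitals, medical history, concomitant medication, AE assessment, photography and other study related procedures mentioned in Table 1".

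**Other non-responder rule.** The only one is in SAP 5.4, for withdrawal through lack of effect before any post-baseline assessment.

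**The concern.** The event that matters to the estimate is the start of another drug that acts on psoriasis. The plan makes the outcome depend on the label attached to that drug. Given as rescue, it is a failure. Obtained elsewhere, it is either a deletion or a carried score.

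Each alternative has its own fault. Deletion removes a randomized patient because of something that happened after randomization and may be related to poor disease control. The major or minor call is also discretionary, and it is finalized when PASI results may already be known. Carrying the last score can assign another drug's effect to the randomized arm. On placebo that narrows the difference; on an AUR101 arm it credits AUR101 with a response it did not produce. With about 2 responders expected among 30 placebo patients (0.07 × 30 = 2.1), one or two such patients can matter.

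**Working it through.** **1. What the text gives each patient**

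| Patient on the same active drug | Efficacy population | Week 12 PASI 75 |
|---|---|---|
| Given as rescue | Kept | Failure (SAP 4.6) |
| Outside rescue, classed major | Removed (SAP 4.3.4) | None |
| Outside rescue, classed minor | Kept | Last PASI carried, no cut-off at first use |

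On the minor route, a score on the drug exists only if a rating falls after first use. This can happen in two ways. Under Protocol 9.5 the PASI is already scored when the drug is disclosed at a visit. Under Protocol 11.4.1.3 a follow-up PASI can fill a missed visit. If no rating follows first use, the score from before the drug is carried.

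**2. The plan's own figure**

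Inputs (SAP 5.1): 7% on placebo, 35% on AUR101, 25 per arm; the plan "will provide an 80% power with a one-sided Type I error of 0.05". With p̄ = (0.07 + 0.35)/2 = 0.21:

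Power = Φ{[0.28√n − z√(2p̄(1−p̄))] / √(0.07×0.93 + 0.35×0.65)}

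At n = 25 and z = 1.645: [1.400 − 1.645×0.576]/0.541 = 0.837, so power is 79.9%. The stated 80% reproduces.

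**3. Effect of outside-drug users**

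The analysis is two-sided (alternatives in SAP 7.1, p<0.05 in SAP 9.1), so the check uses the two-sided 0.05 Pearson chi-square with 30 per arm. AUR101 responders follow Binomial(30, 0.35). Power is the total probability of all pairs of counts with p<0.05.

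Assumptions not in the documents: k = 0 to 3 users, all on placebo, and their response rate on the drug. Placebo responders are then:
- excluded: Binomial(30−k, 0.07) out of 30−k;
- kept, half respond: Binomial(30−k, 0.07) + Binomial(k, 0.5) out of 30;
- kept, all respond: Binomial(30−k, 0.07) + k out of 30.

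| k | Excluded | Kept, 50% respond | Kept, all respond |
|---|---|---|---|
| 0 | 79.8% | 79.8% | 79.8% |
| 1 | 80.4% | 73.6% | 66.3% |
| 2 | 79.2% | 66.9% | 50.7% |
| 3 | 77.5% | 60.0% | 35.7% |

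Expected placebo rates in the last column are [0.07(30−k) + k]/30 = 7.0, 10.1, 13.2 and 16.3%. The slight rise to 80.4% comes from the discreteness of the counts. Under Fisher's exact test, which SAP 7.1 also allows, the last column is 69.2, 54.0, 38.1 and 24.4%.

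**4. One concrete result**

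Take counts near the planned rates, with users counted as failures: 10/30 vs 2/30, Fisher p = 0.021 (chi-square 0.010).
- One placebo user's on-drug response carried: 10/30 vs 3/30, p = 0.057 (chi-square 0.028).
- Two carried: 10/30 vs 4/30, p = 0.125 (chi-square 0.067).
- One or two non-responding placebo users dropped instead: p = 0.021 to 0.022.

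Dropping patients can also shift the estimate. If two AUR101 users who would count as failures are removed, the AUR101 rate moves from 10/30 = 33.3% to 10/28 = 35.7%.

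**The case against.** The strongest reply is that SAP 4.3.5 already deals with these patients. A drug that produces a PASI 75 response plainly meets its definition of a major deviation, so the patient leaves the efficacy population and no score is carried. SAP 5.4 likewise opens its withdrawal rule with patients who have no major deviation. Excluding 1 to 3 placebo users costs almost no power. Rescue is also open early to patients with intolerable symptoms, which reduces the need for outside treatment, and the withdrawal visit in Protocol 7.4 requires only safety assessments.

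Most of this stands. A reader might infer that a placebo patient who reaches PASI 75 on an outside drug is, as the plan is written, a Week 12 responder. The documents do not support that: it requires a rating after first use and a minor classification. Nor do they support reading 35.7 to 66.3% as the expected power, since those figures need every user to be kept and to respond. The documents also do not show that such use would concentrate on placebo. Rating PASI before asking about medication is not a fault in itself; it is only one way in which a score on the drug can come to exist.

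What does not stand is that exclusion settles the matter. It still treats the same drug differently according to route, it still drops randomized patients for a later event, and the individual classification leaves brief or topical use open to either outcome.

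**Conclusion.** The inconsistency is in the text, and neither branch is as sound as one uniform non-responder rule. The likelier branch is exclusion. Its effect on power is small (77.5 to 80.4% against 79.8%), and the objection to it is one of principle and possible selection. The less likely branch, a carried score, can be large: 60.0 to 73.6% if half of the users respond and 35.7 to 66.3% if all do. At the planned rates, one carried placebo responder can move the Fisher p-value across 0.05. All of these figures rest on an assumed 1 to 3 users, all on placebo.

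The rescue side is also incomplete. The protocol synopsis joins treatment failure to LOCF in one sentence, and SAP 5.4 and 7.1 do not repeat the failure rule. The point should be corrected before soft lock; it does not invalidate the design.

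**What to change.** Amend SAP 4.3.4, 4.3.5, 4.6 and 5.4, with Protocol 11.3.2 and 11.4.1.3 to match, so that for any Protocol 8.11 therapy that can affect psoriasis, used during the treatment period as rescue or otherwise:

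- its use is not a reason for exclusion from the efficacy population;
- the patient is a non-responder for the PASI, IGA and DLQI responder endpoints from first use;
- scores on or after first use, including follow-up scores, are not used, and continuous endpoints carry the last score before first use;
- for rescued patients, non-response overrides LOCF for responder endpoints.

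The population and deviation sections must be changed too; otherwise they would still remove these patients.

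The cost is wording in both documents and a comparison of dates with the concomitant-medication data, which are checked at every visit. The downside is that brief, minor topical use also counts as failure and may lower a response rate slightly. A sensitivity analysis excluding such patients would show by how much. This is an analysis rule only and changes no clinical management.
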